6.1.1. Evaluation of Safety

The DSMB will review demographic, baseline, treatment exposure, and safety data, including adverse events, serious adverse events, deteriorations and deaths, which will be

summarized prior to each meeting. Data to be reviewed will include tabulations of aggregate data (all data from all patients grouped), tabulations of unblinded comparative outcome data by treatment group, and by-patient listings.

In the role of safety advisory group for this study, the DSMB will:

- 1) evaluate the incidence of deaths, all adverse events, particularly serious adverse events and those reported with moderate or severe intensity, and other relevant measures of patient safety, patient enrollment and study completion status,
- 2) determine whether a modification or termination of the study is necessary to ensure patient safety or recommend continuing the study,
- 3) monitor the conduct of the study, e.g., rate of recruitment, ineligibility, non-compliance with the protocol, dropouts, and balance between treatments with respect to demographics,
- 4) inspect descriptive statistics of average PAS at baseline and Day 5 and of the change from baseline to Day 5,
- 5) inspect descriptive statistics of secondary outcomes (PCR, HLPE, PDT, FOIS, NIHSS) and change from baseline in secondary outcomes at each visit in which they are measured,
- 6) consider whether the trial or dose should be temporarily or permanently stopped based on pre-defined stopping rules for the number of certain type of adverse events. Specifically:
 - a. pause/stop enrollment in a dose if 3/10 or 4/20 in that dose exhibit seizures;
 - b. pause/stop all enrollment if at least 4/20 or 5/40 patients in both active doses combined experience seizure;
 - c. the mortality stopping rule will be the same as the seizure stopping rule; note that the probability for these rules is based on the following assumptions and on the binomial distribution:
 - i. we assume the natural history of the condition yields probability of seizure of 6% and probability of mortality of 7%;
 - ii. probability of stopping the study for safety, if these are the true probabilities, using the above stopping rules, is $\leq 5\%$;
 - iii. thus if a stopping rule is met, odds are that true rates are higher than 6%/7%;
 - d. a swallowing deterioration for an individual patient is defined as follows: A FOIS change from baseline of ≥ 3 points will trigger a repeat, interim swallowing assessment; swallowing deterioration will then be defined as an increase in the PAS score ≥ 2 points compared to baseline score based on this interim assessment. The stopping rule for a swallowing deterioration is:
 - i. pause/stop enrollment in a dose if 5/10 or 8/20 in that dose exhibit swallowing deterioration;
 - ii. Pause/stop all enrollment if at least 8/20 or 13/40 patients in both active doses combined swallowing deterioration; note that the probability for these rules is based on the following assumptions and on the binomial distribution:
 1. we assume the natural history of the condition yields probability of swallowing deterioration of 20%;

2. probability of stopping the study for safety, if this is the true probability, using the above stopping rules, is $\leq 5\%$;
 3. thus if the stopping rule is met, odds are that true rates are higher than 20%;
- e. a neurological deterioration for an individual patient is defined as a ≥ 4 point worsening from baseline on the NIHSS global impairment score. The same stopping rule for swallowing deterioration will be applied to neurological deterioration.
 - f. A limb deterioration for an individual patient is defined as a ≥ 2 point worsening from baseline on the NIHSS motor score for a given limb. The same stopping rule for swallowing deterioration will be applied to limb deterioration.

These stopping rules will serve as a guideline, not an absolute end-point, for the DSMB to consider stopping the trial.

All reported AEs and AEs considered by the study investigator to be treatment-related (having a relationship of at least possibly study intervention) will be tabulated for all patients who have received any amount of intervention. Tabulations of serious adverse events will be provided. As part of the AE and serious AE tabulations, the incidence of neurological and swallowing deteriorations will be provided. At regularly scheduled meetings the DSMB will be provided with a copy of all SAE Reports. In addition, the DSMB will be notified of any reportable SAEs as soon as possible in between meetings. Any additional information necessary to evaluate the continued safety of all patients enrolled in this trial will also be provided.

Based on differential mortality rate and the type, severity, and relationship of the AEs to study drug, the DSMB may recommend continuation, suspension, modification of procedures, and/or stopping the trial.

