Analytic plan for Secondary Aim: To assess the effect size across subject-specific predictors (baseline NIHSS score, dysarthria, CBT-lesion load and intubation), subgroup analyses will be conducted. For such analysis regression models will be employed that include intervention, covariate and covariate by treatment interactions as predictors and PAS scores, PCR, PDT, HLPE as outcomes, to examine the modifying effect of the covariates on the intervention. If a significant interaction is detected, analyses of major efficacy endpoints (PAS scores, PCR, PDT, HLPE) will be performed within each group.

Missing Data: Many longitudinal studies have the potential to suffer from problems with missing data. We anticipate a 35% - 40% attrition rate in this study, which includes drop-out, spontaneous recovery and discharge, based on review of our hospital records over the past 5 years. Based on experience, we do not expect any other serious problems with either the extent or the pattern of missing data but we will explore this issue by employing multiple imputation methods for handling missing data.

Sample Size and Power Calculations: We plan to enroll and randomize 99 subjects; 33 subjects to each of the two active and sham treatment. With the above sample size, after 40% attrition, we estimate that a difference of 1.0 and 1.15 standard deviations between the active and sham treatment in the mean primary outcome measure of the study can be detected with a type I error rate of 2.5% and power 80% and 90%, respectively. In our pilot study the difference we estimated was 1.35 with an approximate standard deviation for the differences in the two groups of 1.2, with a standardized difference of 1.1 standard deviations. Thus we expect to have $\geq 87\%$ power to detect the expected differences in our study. We also anticipate a greater effect size in the high dose group and thus the power to be greater.

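### The numerical safety guidelines end at 20 patients per dose and 40 active patients, although 33 and 66 are to be randomised

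*Combined protocol and SAP*

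**What the plan says.** Section 6.1.1 (Evaluation of Safety) of the combined protocol and SAP gives these rules:

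- Seizure, per dose: "pause/stop enrollment in a dose if 3/10 or 4/20 in that dose exhibit seizures". Combined: "pause/stop all enrollment if at least 4/20 or 5/40 patients in both active doses combined experience seizure".
- Mortality: "the mortality stopping rule will be the same as the seizure stopping rule".
- Swallowing deterioration, per dose: "pause/stop enrollment in a dose if 5/10 or 8/20 in that dose exhibit swallowing deterioration". Combined: "Pause/stop all enrollment if at least 8/20 or 13/40 patients in both active doses combined swallowing deterioration".
- Neurological deterioration: "The same stopping rule for swallowing deterioration will be applied to neurological deterioration". Limb deterioration: "The same stopping rule for swallowing deterioration will be applied to limb deterioration".

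The assumed background rates are 6% for seizure, 7% for mortality and 20% for swallowing deterioration. The chance of stopping at those rates is put at no more than 5%. The same section calls the rules guidance for the DSMB and not an absolute end-point.

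The sample size paragraph of section 3.1.6 plans "33 subjects to each of the two active and sham treatment", so 66 patients on active stimulation, and expects 35% to 40% attrition. In the same section, the safety analysis covers everyone treated at least once. Section 6.1.1 tabulates adverse events on the same basis.

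**The concern.** Safety is part of the primary aim. Section 2 describes safety data in the acute phase as sparse. Section 3.1.2 says that cut-offs for suspension will come from historical cohorts because the sample is small and few events are expected. The plan therefore chose to give the DSMB numbers to work with. Those numbers run out at 20 and 40 patients while enrolment is planned to continue to 33 and 66, and no reason is given. A moderate excess of events is easier to see as patients accumulate, so the guidance ends before the data are at their most informative. At stake is whether a pause prompted by a pre-specified count could still protect the later patients.

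**Working it through.** **Share enrolled after the last guideline.** Per dose: (33 − 20)/33 = 39.4%. Combined: (66 − 40)/66 = 39.4%. If the counts refer to completers, 40% attrition leaves 33 × 0.60 = 19.8 per dose and 66 × 0.60 = 39.6 active, so nobody is left over. At 35% attrition, 21.45 and 42.9 remain, and the share is 2.9/42.9 = 7%.

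**The charter's 5% claim.** For one look, the false-stop chance is P(X ≥ r) with X ~ Binomial(n, p). Over two looks it is P(X₁ ≥ r₁) + Σ P(X₁ = s) · P(Y ≥ r₂ − s), summed over s < r₁, where Y counts events in the patients added since the first look.

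| Rule (background rate) | Per dose: look 1, look 2 | Per dose, both looks | Combined: look 1, look 2 | Combined, both looks |
|---|---|---|---|---|
| Seizure (6%) | 1.9%, 2.9% | 3.8% | 2.9%, 9.0% | 9.6% |
| Mortality (7%) | 2.8%, 4.7% | 5.9% | 4.7%, 14.5% | 15.4% |
| Swallowing (20%) | 3.3%, 3.2% | 5.2% | 3.2%, 4.3% | 6.1% |

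The per-dose rules meet 5% look by look. Over both looks, mortality and swallowing do not. The 5/40 count exceeds 5% even alone, which is a separate matter but bears on any recalibration.

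**Sensitivity at double the background rate (assumed: 12%, 14%, 40%).** Worked case, seizure per dose at 12%:

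- First look: P(X₁ ≥ 3 of 10) = 0.109.
- P(X₁ = 0, 1, 2) = 0.279, 0.380, 0.233. The matching chances of reaching a total of 4 among the next 10 are 0.024, 0.109 and 0.342.
- Second look adds 0.279 × 0.024 + 0.380 × 0.109 + 0.233 × 0.342 = 0.128.
- Total: 0.109 + 0.128 = 0.236, or 24%.

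The same recursion with a third per-dose look at 33 gives the last two columns. The joint search took whole-number counts at 10, 20 and 33 with an overall false-stop chance of at most 5%, and kept the set with the highest detection.

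| Rule | Combined, as written (both doses affected) | Per dose, as written | Look at 33 by the single-look method: detection (overall false stop) | All three looks held jointly to 5%: detection (overall false stop) |
|---|---|---|---|---|
| Seizure | 54% | 24% | 40% (6.3%) | 36% (4.6%) |
| Mortality | 68% | 33% | 42% (6.8%) | 36% (4.8%) |
| Swallowing | 88% | 62% | 78% (6.1%) | 77% (4.4%) |

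The single-look counts at 33 are 5, 6 and 12. The joint sets at 10, 20 and 33 are 4, 5, 5 (seizure), 3, 5, 6 (mortality) and 6, 8, 12 (swallowing). All are arithmetic illustrations and not proposed rules. Each joint set raises at least one of the present counts at 10 or 20. Keeping the present seizure counts and adding 6/33 would give 30% (false stop 4.3%).

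Neurological and limb deterioration have no background rate of their own in the charter. The swallowing figures carry over only if 20% applies to them.

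**The case against.** Four points can be made on the other side.

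1. **Monitoring does not stop at 20 and 40.** A reader might infer that later patients have no protection. The documents do not support that. The DSMB sees data by group at each meeting, at least yearly (sections 6.1.1 and 7). It receives SAE listings monthly (section 10) and early notice of reportable SAEs. It can hold unscheduled meetings and recommend stopping on general safety grounds (section 9). This stands: what ends is the numerical guidance. But the same discretion exists before patient 20, where the charter still thought numbers useful.

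2. **The last looks match expected completers.** At 40% attrition about 20 per dose and 40 active remain, so the rules may have been sized on completers. The documents do not say. The safety population is everyone treated. Randomisation needs the baseline PAS (section 3.1.1) and the baseline VFSS falls on the first stimulation day (section 3.1.3), so little attrition can precede treatment. The objection makes 39% an upper figure but does not close the gap.

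3. **A look at exactly 33 or 66 comes when enrolment is complete.** The charter's action is to pause or stop enrolment, and none would be left. This stands and shapes the fix.

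4. **The existing rules are more sensitive than the per-dose figures suggest.** The combined rules run alongside them and are met far more often if both doses are affected. This also stands.

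**Conclusion.** The concern holds in a limited form. The pre-specified numerical guidelines for all five event types end at 20 per dose and 40 combined, while 33 and 66 are to be randomised. Up to 39% of active patients are enrolled after that point; the figure assumes that all randomised patients are treated and counted.

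The benefit of extending the rules is moderate. A reader might take 40%, 42% and 78% as what a look at 33 would achieve. Those figures rest on counts whose overall false-stop chance is 6.1% to 6.8%, above the charter's limit. Held jointly to 5%, per-dose detection rises from 24% to 36% (seizure), 33% to 36% (mortality) and 62% to 77% (swallowing). The mortality gain is small. Looks placed before 33 rest on fewer patients, so these figures indicate scale and do not forecast what the fix would deliver.

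The results assume doubled background rates, independent patients and looks taken exactly at the stated numbers.

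**What to change.** - Have the DSMB and the independent biostatistician extend each guideline through planned enrolment. Use a running count, or looks placed between 20 and 33 per dose and between 40 and 66 combined, so that a pause can still protect patients. The organizational meeting in section 7, which is to agree the stopping rules, is the natural occasion. The DSMB sets the counts.
- Calibrate all looks jointly to the charter's stated limit of 5%, and report the resulting false-stop chance for each rule over all its looks.
- State the denominator. Treated patients would match the safety population in section 3.1.6 and the adverse event tabulations in section 6.1.1.

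The cost is charter wording and a modest calculation, with no change to sample size or treatment. There is a real trade-off. The per-dose mortality and swallowing rules and all three combined rules already exceed 5% over their existing looks. Holding to 5% therefore means resetting some earlier counts, with some loss of early sensitivity. The alternative is to state and accept a slightly higher chance of pausing without true harm.

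### The study-level seizure and mortality stopping rule is met by chance in 9.6% and 15.4% of trials, not in 5% or fewer as the charter states

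*Combined protocol and SAP*

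**What the plan says.** All of the relevant text is in section 6.1.1 (Evaluation of Safety), item 6.

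- **Dose-level seizure rule, 6(a):** "pause/stop enrollment in a dose if 3/10 or 4/20 in that dose exhibit seizures".
- **Study-level seizure rule, 6(b):** "pause/stop all enrollment if at least 4/20 or 5/40 patients in both active doses combined experience seizure".
- **Mortality, 6(c):** "the mortality stopping rule will be the same as the seizure stopping rule".
- **Basis, 6(c):** "note that the probability for these rules is based on the following assumptions and on the binomial distribution". Under 6(c)(i), "we assume the natural history of the condition yields probability of seizure of 6% and probability of mortality of 7"%.
- **Claimed property, 6(c)(ii):** "probability of stopping the study for safety, if these are the true probabilities, using the above stopping rules, is $\leq 5"%. Item 6(c)(iii) then concludes that meeting a rule makes it likely that the true rates exceed 6% and 7%.
- **Swallowing deterioration, 6(d):** a dose-level rule of 5/10 or 8/20, and at study level "Pause/stop all enrollment if at least 8/20 or 13/40 patients in both active doses combined swallowing deterioration". The assumed rate is 20%, with the same claim of 5% or less. Items 6(e) and 6(f) reuse this rule for neurological and limb deterioration.
- **Status:** "These stopping rules will serve as a guideline, not an absolute end-point, for the DSMB to consider stopping the trial".

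**The concern.** Item 6(c)(ii) states an operating characteristic that can be recomputed from the charter's own inputs, and the counts look too low to deliver it. At 6% one expects 40 × 0.06 = 2.4 seizures among 40 patients, and at 7% one expects 2.8 deaths. A boundary of 5 is not far above either. The two events also share one set of counts although mortality is assumed to be more frequent, so mortality must do worse than seizure.

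The figure matters because it tells DSMB members how surprised to be when a boundary is crossed, and 6(c)(iii) builds its inference on it. Section 7 asks the organizational meeting to agree the stopping rules. If the figure is wrong, members agree to a false-alarm rate that the rules do not have, and a pause prompted by chance could delay a single-centre trial of 99 patients.

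**Working it through.** **Inputs, all from section 6.1.1, item 6.** Study-level boundaries are at least 4 of 20 or at least 5 of 40, active doses pooled. True rates are p = 0.06 (seizure) and p = 0.07 (mortality). Counts are binomial. The claim to reproduce is a stopping probability of 5% or less.

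**Step 1: each look alone.** P(X ≥ r) = 1 − Σ C(n,x) pˣ (1−p)ⁿ⁻ˣ, summed over x = 0 to r−1.

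For n = 40, r = 5:

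- p = 0.06: 1 − (0.0842 + 0.2149 + 0.2675 + 0.2162 + 0.1277) = 9.0%
- p = 0.07: 1 − (0.0549 + 0.1652 + 0.2425 + 0.2312 + 0.1609) = 14.5%

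For n = 20, r = 4, the same formula gives 2.9% and 4.7%. The 20-patient look therefore meets the claim, and the 40-patient look does not.

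**Step 2: the rule as written, either look.** With X₂₀ the count in the first 20 patients and Y the count in the next 20,

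P(stop) = P(X₂₀ ≥ 4) + Σ P(X₂₀ = x) · P(Y ≥ 5 − x), summed over x = 0 to 3.

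- Seizure: 0.0290 + [0.2901×0.0056 + 0.3703×0.0290 + 0.2246×0.1150 + 0.0860×0.3395] = 0.0290 + 0.0674 = **9.6%**
- Mortality: 0.0471 + [0.2342×0.0107 + 0.3526×0.0471 + 0.2521×0.1610 + 0.1139×0.4131] = 0.0471 + 0.1068 = **15.4%**

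**Step 3: can another reading give 5% or less for both events?**

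| Reading | Seizure | Mortality | Fits the text? |
|---|---|---|---|
| 40-patient look only, 5 or more | 9.0% | 14.5% | Yes, but ignores the 20-patient look |
| 40-patient look only, more than 5 | 3.1% | 5.8% | No, the rule says at least 5 |
| Both looks, strictly more than 4 and 5 | 3.2% | 6.0% | No, same reason |
| Normal approximation, 5/40, no continuity correction | 4.2% | 8.6% | No, binomial is specified |
| Counts met in each dose separately | 0.9% | 2.4% | No, the doses are pooled |

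Only the last row is at or below 5% for both, and it contradicts the pooling. With the present counts, 5% would need a true rate of about 5.1% (40-patient look alone) or 4.9% (both looks).

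**Step 4: the other rules, same formulas.**

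| Rule | Assumed rate | First look | Second look | Either look |
|---|---|---|---|---|
| Dose level, 3/10 or 4/20, seizure | 6% | 1.9% | 2.9% | 3.8% |
| Dose level, 3/10 or 4/20, mortality | 7% | 2.8% | 4.7% | 5.9% |
| Dose level, 5/10 or 8/20, swallowing | 20% | 3.3% | 3.2% | 5.2% |
| Study level, 8/20 or 13/40, swallowing | 20% | 3.2% | 4.3% | 6.1% |

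**Step 5: wider figures, for context only.** Counting any trigger, in either dose or pooled, and assuming 10 and then 20 patients per dose at aligned looks, simulation gives 11.8% (seizure), 18.0% (mortality) and 11.8% (swallowing). If seizure and mortality were independent, at least one of the two study-level rules would be met with probability 1 − (1 − 0.0964)(1 − 0.1539) ≈ 24%.

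**The case against.** The strongest reply concerns consequence, not arithmetic. The charter says the rules guide the DSMB and do not bind it, and they call for a pause or a stop. So 9.6% and 15.4% are chances of prompting a DSMB discussion, not of ending the trial. The DSMB also sees data by treatment group and may act on differential mortality, so a chance excess would be read beside sham. The error leans toward caution, and it does not touch the efficacy analysis or the sample size. All of this stands and limits the harm. None of it makes the stated figure true, and members using an advisory boundary need to know how often chance crosses it.

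A second reply is that the inference in 6(c)(iii) can still be reasonable. Five of 40 is 12.5%, about double the assumed rates. Under a Jeffreys prior (an assumption, not in the charter), the posterior probability that the true rate exceeds 6% is about 95%, and that it exceeds 7% about 91%. This also stands. The sentence need not be deleted, but it should not be presented as following from a 5% figure that is wrong.

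Third, the swallowing rule meets 5% at each look and misses only cumulatively, and the charter does not say which is meant. That is fair, and the 1.1-point excess is minor. Fourth, the any-trigger figures go beyond a claim about stopping the study and assume a look schedule that the charter does not give. The 24% assumes independence, which is doubtful because section 3.1.2 counts deaths from seizure as stroke-specific mortality. Neither is needed for the conclusion.

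**Conclusion.** The concern holds. On the charter's own rates and distribution, the study-level rule is met by chance with probability 9.6% for seizure and 15.4% for mortality. That is about two and three times the stated ceiling, and for mortality about one harmless trial in six or seven. The result does not depend on how multiple looks are counted, because the 40-patient boundary alone gives 9.0% and 14.5%. It rests on independent patients with a constant event rate, as the charter's binomial model implies, and on looks at 20 and 40 pooled active patients.

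The swallowing rule is a lesser matter: correct at each look, 6.1% over both. Because the rules are advisory and err toward stopping, this is a wrong statement about a decision threshold rather than a threat to patients or to the efficacy conclusions. It should still be corrected before the DSMB relies on it.

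**What to change.** Either of two changes is enough.

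1. **Keep the counts and correct the statement.** In 6(c)(ii), replace the 5% claim with the exact probabilities for the two-look rule: 9.6% for seizure and 15.4% for mortality. In 6(d)(ii)(2), give 3.2% and 4.3% for the two looks and 6.1% overall. Reword 6(c)(iii), and the parallel line for swallowing, so that the inference no longer follows from the 5% figure.
2. **Keep the 5% ceiling and change the counts.** The DSMB statistician should derive the counts jointly over both looks, and separately for the 6% and 7% rates. Two-look probabilities for some candidates:

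| Study-level rule | Seizure, 6% | Mortality, 7% |
|---|---|---|
| 4/20 or 6/40 | 4.8% | 8.2% |
| 4/20 or 7/40 | 3.3% | 5.6% |
| 5/20 or 6/40 | 3.2% | 6.0% |
| 5/20 or 7/40 | 1.2% | 2.5% |

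Of these, only 5/20 or 7/40 keeps both events within 5%. With separate counts, 4/20 or 6/40 would serve for seizure. Higher counts make the rule slower to react to a real excess, so the choice belongs to the DSMB.

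Under either option, the charter should say whether the quoted probability is per look or cumulative. The cost is a wording change and a one-page exact-binomial table. Under the first option, the stated figure becomes less favourable.
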